6. STUDY PROCEDURES AND ASSESSMENT

6.1. DEFINITIONS OF STUDY PROCEDURES

6.1.1. Informed Consent

Prior to initiation of any study procedures, each subject will undergo an Informed Consent process in which the subject voluntarily confirms their willingness to participate in the trial, after having been informed of all aspects of the trial relevant to their decision to participate. The investigator, or a person designated by the investigator, will fully inform the subject of all pertinent aspects of the trial. In addition, the investigator, or a person designated by the investigator, will inform the subject that he is free to refuse to enter the study or to withdraw from the study at any time, for any reason.

The Informed Consent Form (ICF) approved by the IRB/EC will contain a description of the study's purpose, procedures, inconveniences and potential risks, and anticipated benefits.

Prior to a subject's participation in the trial, an ICF will be signed and personally dated by the subject and by the person who conducted the Informed Consent discussion.

If a subject is unable to read, he may not participate in the study.

Prior to participation in the trial, the subject will receive a copy of the signed and dated written ICF. During participation in the trial, the subject will receive a copy of the signed and dated consent form updates and a copy of any amendments to the written information provided to subjects.

The investigator should document in the source data that the Informed Consent was signed prior to subject's participation in the study and according to the International Conference on Harmonization Good Clinical Practice (ICH-GCP) guidelines, as described above.

6.1.2. Medical History

Subjects' medical history should be fully documented at Screening Day (45 through 1 day prior to baseline), to ensure compliance with study inclusion criteria and the absence of circumstance mentioned in the exclusion criteria. Medical history information must include, but not be limited

to, past and present medical conditions, concomitant non-drug treatments and hypersensitivity to drugs.

6.1.3. Concomitant Medication

All concomitant medication given 1 month prior to study entry, including blood and blood products, dietary supplements, and non-prescription drugs will be listed at screening/baseline. Each entry will include the treatment's start date, treatment name (Generic), reason for use, dosing regimen (dose and frequency of use), route of administration, and stop date (if applicable). The clinical significance of the medication use will be decided by the investigator. Study subjects will be routinely questioned for changes in the administration of concomitant medication during the trial and changes should be updated from medical records as well.

6.1.4. Physical Examination

The investigator (or medically qualified nominee) will conduct a complete physical examination, at Screening Day (performed 45 through 1 days prior to baseline). Additional examination that will be performed during screening will include height and weight measurements to determine BMI in order to ensure compliance with study criteria. A skin type score using Fitzpatrick Skin Type will be performed. Skin type will be assessed prior to injection in order to determine skin sensitivity to treatment.

The Fitzpatrick scale is based on 6 categories of skins as described below:

Type I	Light, Pale white	Always burns, never tans
Type II	White, fair	Usually burns, tans with difficulty
Type III	Medium, white to olive	Sometimes mild burn, gradually tans to olive
Type IV	Olive, moderate brown	Rarely burns, tans with ease to a moderate brown
Type V	Brown, Dark brown	Very rarely burns, tans very easy
Type VI	Black, very dark brown to black	Never burns, tans very easily, deeply pigmented

6.1.5. Weight Measurement

Weight measurement will be performed at screening visit to determine BMI value prior to injection. An additional weight measurement will be performed at Baseline visit and on study visits at Day 56 and 84 following injection to verify that there are no significant changes in weight throughout the assessment of submental fat changes during the study.

6.1.6. Vital Signs Measurements

Subjects' vital signs will be measured at Screening Day (performed 45 through 1 days prior to baseline) in order to ensure compliance with study inclusion criteria.

Vital signs measurements will include systolic and diastolic sitting position blood pressure, pulse rate, respiratory rate, and body oral temperature.

Additional vital signs measurements to assess subject's safety will be performed at baseline visit (Day 0) prior to drug injection, the following day (Day 1) after drug injection and on study visits 7, 14, 28, and 56 days following injection.

6.1.7. Draize Score

Subjects' skin irritancy will be evaluated by Draize score at baseline visit prior to injection in order to establish a baseline to compare following drug injection.

Additional skin irritancy evaluation to assess subject's safety will be performed at baseline visit $2 \text{ hours} \pm 30 \text{min}$ following injection, on the following visits days: 1, 7,14, 28, 56, and 84.

Skin irritancy observations in the injected sites and contra-lateral sites will be scored using the Draize scale for scoring skin reaction:

Erythema and eschar formation		Edema formation	
No erythema	0	No edema	0
Very slight erythema (barely perceptible)	1	Very slight edema (barely perceptible)	1
Well defined erythema	2	Slight edema (edges are well defined by definite raising)	2
Moderate to severe erythema	3	Moderate edema (raised approximately 1mm)	3
Severe erythema (beet redness) to slight eschar formation (injuries in depth)	4	Severe edema (raised more than 1mm extending beyond area of exposure)	4

6.1.8. 2D Standardized Photography

Standardized photography (2 dimensional) of the face (submental fat area) will be applied at baseline visit prior to treatment in order to establish a baseline to compare following drug injection.

Additional photography will be conducted on Days: 7, 14, 28, 56, and 84 to evaluate qualitative changes in submental fat area at study follow ups and to assist physician and subjects to assess treatment efficacy and satisfaction by comparison of images taken at each study visit vs. screening visit.

Photographs will be taken with digital camera according to photography standards in dermatology surgeries for the face/neck area (See Appendix II).

Lateral and anterior images of the face will be taken.

6.1.9. MRI

The aim of the MRI exam is to evaluate fat reduction before and following treatment. MRI exams will be conducted in imaging centers close to selected clinical sites.

MRI will be conducted to all subjects enrolled into the study, at Screening Day (performed 45 through 1 day prior to baseline) in order to establish a baseline to compare at study endpoint, and at Day 84.

MRI (performed during screening period) will be conducted after subject qualifies on all screening criteria within a window of 5 days from the visit in the clinic. Post-treatment period MRI will be completed 84 days (\pm 5 days) after the subject's last treatment session.

Quantitative measurements such as fat volume of the submental fat area will be used as an objective parameter for submental fat reduction before and following treatment.

Sagittal 2D and 3D images of the head and neck (chin area) will be obtained using 1.5 Tesla machine (General Electric or Siemens or Phillips). For each MRI acquisition visit, the total imaging time is expected to be approximately 30 minutes.

During the imaging, subjects will be positioned in Head first Supine recumbent. Images in the sagittal plane across the entire submental region will be collected using an appropriate MR sequence to minimize the effects of air cavities, dental implants, and amalgam on the resultant MR image. This imaging approach will generate a 2D and 3D image data set that allows for the quantification of the submental fat volume in several slices covering the treatment area. In the follow up MRI exam slices will be positioned as similar as possible to the first MRI exam. MRI will be performed according to a detailed written manual.

Images should be saved in a DICOM format with the information of date and subject's screening number to be transferred by the Sponsor's request for central analysis.

Submental volume analysis will be performed by computer-assisted tools to delineate the tissue boundaries and limits of the submental region and calculation of submental volume will be done before and following RZL-012 injection.

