3. STUDY DESIGN

3.1. DESCRIPTION OF STUDY DESIGN

This is a single blinded, randomized, placebo-controlled, 2-cohort, clinical study in healthy volunteers.

Cohort 1 will be comprised of 8 active (RZL-012) and 4 placebo subjects. Cohort 2 will be comprised of 16 subjects. That will be randomized to receive active or placebo treatment All subjects will receive a single dose of RZL-012 or vehicle into the submental fat, after which they will be monitored for safety and efficacy assessments across 84 days of follow-up. All subjects per cohort will be randomized to either active treatment or placebo at a ratio of 2:1 per cohort. Subjects will be blinded to study treatment while physicians will not be blinded.

The study will be composed of 2 treatment cohorts, 12 subjects at cohort 1 and 16 subjects at cohort 2.

A total of 28 subjects will be treated in 2 clinical sites.

At cohort 1, a total of 12 subjects will be randomized to receive active or placebo treatment (2:1) according to randomization program that will be prepared prior to study initiation. At cohort 2, 16 subjects will be randomized to receive active or placebo treatment. Each clinical site will have at least one active and one placebo treatment subject per each study cohort. In case of slow enrollment in one of the sites, other sites may complete the enrollment of subjects in each cohort.

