6.1.15.2.2. MRI to calculate volume changes of submental fat

MRI will be conducted at Screening Visit and on Day 84 visits to quantitively assess a change or reduction from baseline in submental fat dimensions (volumetric measurement).

MRI (performed during screening period) will be conducted after subject qualifies on all screening criteria within a window of 5 days from the visit in the clinic. Post-treatment period MRI will be completed 84 days (± 5 days) after the subject's last treatment session.

Lower volume is expected to be measured 84 days following treatment among RZL-012 treated subjects and no change or minor change in submental fat volume is expected in placebo treated subjects. This will be served as an objective parameter to assest reatment efficacy.

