6.2.2. Study Randomization

Subjects will be randomized to each study group, i.e., investigational therapy or control, according to a predefined randomization scheme in a ratio of 2:1 (active:placebo) among the

2 clinical sites and per each study cohort. The investigational therapy group will be treated with RZL-012 and the control group will be treated with the same formulation (vehicle) as with RZL-012, absent active medication.

Assignment to study group will be disclosed only after subject eligibility is confirmed and immediately before treatment initiation. The investigator and clinical staff will be unmasked and will be responsible to fill the syringes for injection. The subject will be blinded and will not know whether he is injected with active or placebo treatment.

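### MRI files go to central analysis labelled with the scan date, and no reader masking is stated, so visit order is exposed on the trial's only objective efficacy measure

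*Combined protocol and SAP*

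**What the plan says.** Section 6.1.9 specifies the label on each image file, beginning "Images should be saved in a DICOM format with the information of date", and then the rest of the label and its route: "with the information of date and subject's screening number to be transferred by the Sponsor's request for central analysis". On reading it says: "Submental volume analysis will be performed by computer-assisted tools to delineate the tissue boundaries and limits of the submental region". It says of quantities such as fat volume that they "will be used as an objective parameter for submental fat reduction before and following treatment". Sections 6.1.9 and 6.1.15.2.2 and Appendix I place MRI at two times only, screening and Day 84. Section 6.1.15.2.2 gives the expected result: "Lower volume is expected to be measured 84 days following treatment among RZL-012 treated subjects", with little or no change on placebo.

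On blinding, Section 3.1 says: "Subjects will be blinded to study treatment while physicians will not be blinded". Section 6.2.2 adds: "The investigator and clinical staff will be unmasked". No section mentions masking of the person who reads the MRI, either to treatment or to the order of the two scans. Section 6.1.9 refers to a written manual for performing the MRI, which is not among the documents.

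Section 4.2 lists three efficacy endpoints, all secondary: the physician's global assessment, MRI fat volume, and FACE-Q satisfaction. Sections 10.5.1 and 10.5.5 plan to tabulate the mean change in volume by treatment and cohort.

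**The concern.** Drawing the limits of a fat compartment leaves room for judgement unless it is fully automated, and the plan calls it computer-assisted, not automatic. A reader who knows which scan came after treatment, and which way the volume is expected to move, can place borderline tissue accordingly without intending to.

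This matters because MRI volume is the only objective efficacy measure. The global assessment is graded by a physician who knows the treatment. FACE-Q is completed by blinded subjects but is subjective. Calipers are used only at screening (6.1.13). The sponsor's earlier MRI reductions came from a double-blind trial (1.2.4.1.2). Here the blind covers subjects only, so reader masking cannot be taken as implied by the design.

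**Working it through.** The plan states no reader error, SD, effect size or power for MRI volume, so it has no figure to reproduce.

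**1. What the label reveals.** There is one scan before treatment and one after, so the scan date identifies the Day 84 scan. The label does not include the treatment arm.

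**2. What each kind of knowledge does to the result.** Let the reader add a shift *s*A to the measured change in the active arm and *s*P in the placebo arm.

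- Reported change, active = true change + *s*A
- Reported change, placebo = true change + *s*P
- Reported difference = true difference + (*s*A − *s*P)

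If the reader knows only visit order and shifts both arms equally, *s*A = *s*P. The difference is then unbiased, but each arm's mean change is off by the shift. If the reader also knows or infers the arm, *s*A and *s*P can differ and the difference is biased.

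**3. Size against the sponsor's earlier effects.** Section 1.1.1 gives Day 56 reductions in abdominal fat-mass ratio of 8.6% (80 mg), 10.5% (120 mg) and 18.1% (180 mg), and a 3.6% increase on vehicle. A shift in one arm biases the difference between arms, so the comparator is the effect against vehicle. The shift of 3 to 5 points is an assumption.

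| Earlier dose | Effect against vehicle | 3-point shift | 5-point shift |
|---|---|---|---|
| 80 mg | 8.6 + 3.6 = 12.2 | 3/12.2 = 25% | 5/12.2 = 41% |
| 120 mg | 10.5 + 3.6 = 14.1 | 3/14.1 = 21% | 5/14.1 = 35% |
| 180 mg | 18.1 + 3.6 = 21.7 | 3/21.7 = 14% | 5/21.7 = 23% |

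The range is about 14% to 41%.

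**4. Size in SD units, if a test were run.** Assume no true effect and a shift of *b* SD of the volume change in the active arm only. For a two-sided 5% two-sample t-test, the noncentrality is *b* × √(nA·nP/(nA + nP)), with nA + nP − 2 degrees of freedom. Cohort 1 is 8 v 4 (3.1). Cohort 2 is taken as 12 v 4, since 10.3 requires at least 4 placebo subjects. Pooled, that is 20 v 8.

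| Comparison | Noncentrality at *b* = 0.5 | False-positive rate, *b* = 0.5 | *b* = 1.0 |
|---|---|---|---|
| Cohort 1, 8 v 4 | 0.5 × √(32/12) = 0.82 | 11.5% | 31.5% |
| Cohort 2, 12 v 4 | 0.5 × √(48/16) = 0.87 | 12.7% | 36.5% |
| Pooled, 20 v 8 | 0.5 × √(160/28) = 1.20 | 21.0% | 63.4% |

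At *b* = 0.25 the pooled rate is 8.9%. Taking cohort 2 as 11 v 5 (nearest to 2:1) changes the pooled figure at *b* = 0.5 to 22.2%.

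For visit order alone, consider a one-sample test of change within an arm of 8. A 0.5 SD shift gives noncentrality 0.5 × √8 = 1.41 and a rejection rate of 23.2% when nothing has changed.

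**The case against.** The strongest reply is that the text shows an omission, not a known bias. Section 6.1.9 says how images are saved and transferred. It does not say what the reader sees, and files could be re-coded on receipt. The manual, which cannot be checked here, may cover this. Scans are made at imaging centres and analysed centrally, away from the unmasked site staff. Computer assistance narrows the reader's discretion. The primary objective is safety, escalation depends on safety data, and the analysis is mainly descriptive, with no test specified for MRI. All of this is fair. It limits the consequence and makes the false-positive rates above illustrations only. It does not supply the missing masking rule, and the one labelling rule that is written exposes visit order.

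A reader might infer more than the documents support:

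- *That no efficacy measure is protected from expectation.* FACE-Q is completed by blinded subjects. It is subjective, but its comparison between arms is masked by design.
- *That the reader is told the arm, or that sponsor staff are unmasked.* The file lists date and screening number only. Sections 3.1 and 6.2.2 unmask physicians, the investigator and clinical staff. Sponsor masking is simply not stated.
- *That the date alone biases the comparison with placebo.* An equal shift in both arms cancels. One caution remains. Sections 1.1.1 and 1.2.1.1 describe fibrotic replacement of fat, prominent at 12 weeks in pigs. If that shows on the Day 84 scan, it could hint at the arm, and the shift need not then be equal.
- *That the bias could be 17% to 58% of the earlier effects.* That comes from dividing by the active-arm reductions alone (3/18.1 and 5/8.6), which leaves out the vehicle change.

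**Conclusion.** The point holds as a gap in protection. As written, the plan exposes visit order to the MRI reader and does not state masking to treatment, on the only objective efficacy measure. Each arm's reported mean change from baseline is open to bias from visit order. The RZL-012 versus placebo difference is open to bias if the reader knows or infers the arm.

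The 14% to 41% rests on an assumed 3 to 5 point shift in the active arm and on Day 56 abdominal fat-mass ratios, which are a different site, measure and time from submental volume at Day 84. The false-positive rates rest on an assumed shift in SD units and on a test the plan does not commit to. Neither is an estimate of what would happen in this trial. Since the trial's efficacy output is mainly a table of mean changes, the change should be made before any scan is read.

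**What to change.** Add to Section 6.1.9:

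- Before central reading, the scan date, visit and screening number are replaced by a random code, both in the file name and in the information stored with the image.
- Both scans of each subject are read in random order by a reader masked to arm, visit and site.
- The code is opened only after all volumes are locked.

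If the MRI manual already requires this, a cross-reference is enough. Matching the follow-up slice position to the first scan is done when the image is acquired, so it does not conflict with masked reading.

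The cost is a small re-coding task for data management. The reader, the number of scans and the sample size stay the same. If masking works, the differential shift in the illustration is zero and the error rate returns to 5%. Re-coding cannot hide a tissue change that is itself visible on the scan, so that risk is reduced, not removed.

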6.1.10. Subject's Satisfaction Rating following Treatment

Subject's satisfaction questionnaire will be collected by use of FACE-Q questionnaire (Copyright©2013 Memorial Sloan-Kettering Cancer Center, New York, USA), at baseline visit prior to injection and at posttreatment follow up visits Day 28, 56, and 84.

The questionnaire will be filled following a comparison of 2D images taken at each time point and comparison to the images taken at baseline visit, prior to injection of RZL-012

The comparison of the images at each study visit vs. baseline will be done by displaying the images of the images of the visit day vs. baseline on the computer.

The FACE-Q questionnaire includes a list of 10 questions related to the chin visibility and degree of subject's satisfaction from his/her chin at each question. Some of the scores reflect a better outcome. A Conversion Table to convert the raw scale summed score into a score from 0 (worst) to 100 (best). See Appendix III for conversion table of FACE-Q questionnaire.

The list of the questions of Face-Q questionnaire is described below:

		Very Dissatisfied	Somewhat Dissatisfied	Somewhat Satisfied	Very Satisfied
a.	The style of your chin (e.g. masculine or feminine)?	1	2	3	4
b.	The size of your chin?	1	2	3	4
c.	The width of your chin?	1	2	3	4
d.	How well your chin suits your face?	1	2	3	4
e.	How sculpted your chin looks (e.g. well defined)?	1	2	3	4
f.	The shape of your chin?	1	2	3	4
g.	How your chin looks in profile (side view)?	1	2	3	4
h.	How your chin looks in photos?	1	2	3	4
i.	How your chin projects compared to the rest of your face?	1	2	3	4
j.	How your chin looks from every angle ?	1	2	3	4

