to the additional 16 subjects of Cohort 2. These subjects will be injected with a maximal dose of 240 mg/subject or with up to 4.8 mL of vehicle. In case of serious safety concerns (e.g., prolonged severe swelling or severe pain following injection) among Cohort 1 subjects receiving the 120 mg dose, sponsor and DSMB may decide to reduce or stay with the 120 mg/subject dose level for Cohort 2 subjects. Subjects will be injected with RZL-012 or vehicle perpendicularly (90°) to the skin. An ice pack will be placed on the injected area for pain relief immediately after injection. Subjects will have to remain seated in the injection position for an additional 10 minutes after dosing. Study Activities upon study entry will include: Procedure Informed consent, medical history, physical examination, measurement of submental skin fold thickness with calipers, weight measurements, vital signs, MRI. Subjects will be randomized upon eligibility to RZL-012 or placebo at each clinical site and each cohort according to a predefined randomization scheme. Periodic site visits will allow assessment of treatment safety (skin adverse events) and efficacy. Subjects will be advised to continue their regular diet and physical activity. Subject site visits will be performed ± 1 days from scheduled dates (from Day 7 visit to Day Visit Schedule 84 visit). Screening visit (Day -45 through -1): Following signing the informed consent - assessment of subject eligibility will include: medical history, physical examination, weight measurements, height measurement, BMI record, pregnancy elimination by women subjects, vital signs, measurement of submental fat thickness using calipers, skin type by Fitzpatrick scale MRI will be conducted within a window of 5 days from the screening visit but prior to baseline visit. **Baseline visit (Day 0):** Pre-treatment: eligibility confirmation, concomitant medications, vital signs, weight measurement, Pregnancy test, Draize score of the injection site area, pain, bruising and induration grading, FACE Q questionnaire, 2D Photography. Treatment - All injections will be administered 90° to the skin surface using a 0.5 mL (cohort 1) syringe or 1 mL (cohort 2) Luer-lock syringe and a 29/30 G x 1/2" needle, respectively (the hole of the needle pointing into the fat layer). The injection pattern will be performed according to physician evaluation of submental fat fullness. At the end of treatment, subjects will remain seated for an additional 10 minutes in the same position. Post treatment: Draize score (2h post injection \pm 30 min), adverse events (AEs) record (including pain, bruising and induration grading). Schedule visits (Day 1-84): At Day 1 following treatment: Concomitant medications, vital signs, Draize score, AEs (including pain, bruising and induration grading). At Days 7 and 14 following treatment: Concomitant medications, vital signs, Draize score, 2D photography of face, AEs (including pain, bruising and induration grading). At Day 28 following treatment: Concomitant medications, vital signs, Draize score, 2D photography of face, Subject's satisfaction questionnaire (Face Q), Physician's global assessment questionnaire, AEs (including pain, bruising and induration grading). At Day 56 following treatment: Concomitant medications, vital signs, weight. Draize score, 2D photography of face, Subject's satisfaction questionnaire (Face Q), Physician's global assessment questionnaire, AEs (including pain, bruising and induration grading). Day 84 visit: Concomitant medications, Weight, Draize score, 2D photography of

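### Follow-up FACE-Q is answered after a baseline-versus-current photograph display that cannot exist at baseline, so within-arm change from baseline can include image cueing

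*Combined protocol and SAP*

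**What the plan says.** Section 6.1.10 schedules the FACE-Q "at baseline visit prior to injection and at posttreatment follow up visits Day 28, 56, and 84". It gives one rule for how the form is answered: "The questionnaire will be filled following a comparison of 2D images taken at each time point and comparison to the images taken at baseline visit". The comparison is made by "displaying the images of the images of the visit day vs. baseline on the computer". No separate rule is given for the baseline administration.

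Section 6.1.8 gives the purpose of the follow-up photographs: "to assist physician and subjects to assess treatment efficacy and satisfaction by comparison of images taken at each study visit vs. screening visit". The same section and Appendix I place the first photograph at the baseline visit, before treatment. No photograph is scheduled at screening.

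The ten items in 6.1.10 are rated from very dissatisfied to very satisfied. Each asks about the chin as it is; none asks about change since treatment. The raw sum (10 to 40) is converted to a 0 to 100 score by Appendix III.

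Sections 4.2 and 6.1.15.2.3 define the endpoint as improvement from baseline in RZL-012 subjects compared with placebo subjects. Sections 10.5.1 and 10.5.5 plan a table of mean change from baseline by treatment, cohort or dose group, and overall. No between-arm model or estimate for the FACE-Q is specified. Under 3.1 and 6.2.2 subjects are blinded, while "The investigator and clinical staff will be unmasked".

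**The concern.** A change from baseline in a status questionnaire can be read as change only if both scores are obtained in the same way. Here the follow-up answer comes after an explicit then-versus-now prompt and the baseline answer cannot. The gap between the two scores can then reflect the prompt as well as the chin. Item h (appearance in photographs) and item g (profile) are the most directly exposed, because 6.1.8 has lateral and anterior images taken.

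The within-arm change is at stake first. The plan is mainly descriptive, so a reader of the planned tables will see the mean change in each arm, and any cueing enters that figure in full. The between-arm contrast is at stake only if the cue works differently in the two arms.

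**Working it through.** The documents give no FACE-Q effect size, standard deviation or power, so there is no planned figure to reproduce. The check has two parts.

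**1. Can the conditions match under the current text?**

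- Baseline FACE-Q: before injection on Day 0 (6.1.10). Earliest photograph: the same visit (6.1.8, Appendix I). No earlier image exists to pair with it.
- FACE-Q at Days 28, 56 and 84: after the visit-day and baseline images are displayed together (6.1.10).

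The mismatch follows from the schedule alone. It does not depend on the order in which procedures are listed.

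**2. What would an assumed cue do to the score?**

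Inputs from Appendix III: raw 20 converts to 37, 21 to 39, 22 to 40, 23 to 42, 30 to 60, 31 to 63, 32 to 67, 33 to 70. Assumptions: a baseline raw sum of 20 in both arms, no true change on placebo, a true gain of 10 raw points on active, and an equal upward cue of c raw points at follow-up in both arms.

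- Placebo change = score(20 + c) − score(20)
- Active change = score(30 + c) − score(20)
- Difference = active change − placebo change

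| c | Placebo change | Active change | Difference |
|---|---|---|---|
| 0 | 37 − 37 = 0 | 60 − 37 = 23 | 23 |
| 1 | 39 − 37 = 2 | 63 − 37 = 26 | 24 |
| 2 | 40 − 37 = 3 | 67 − 37 = 30 | 27 |
| 3 | 42 − 37 = 5 | 70 − 37 = 33 | 28 |

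A shift of +2 corresponds to items g and h each moving up one category; +3 needs a further item. If there is no true change in either arm, both changes equal the placebo column and the difference is 0 for every c. The drift from 23 to 28 arises because the conversion is steeper between 30 and 33 than between 20 and 23.

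Sensitivity to the starting point: over raw sums from 15 to 34, a shift of +2 adds 3 to 7 converted points and a shift of +3 adds 5 to 10.

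Sensitivity to direction: a downward cue of 2 raw points at a raw sum of 20 gives score(18) − score(20) = 33 − 37 = −4.

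Cue added directly on the 0 to 100 scale, with an assumed true difference of 10: an equal cue of 5 gives (10 + 5) − (0 + 5) = 10, unchanged. A cue of 10 on active and 5 on placebo gives (10 + 10) − (0 + 5) = 15.

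**The case against.** The strongest reply is that the endpoint is RZL-012 against placebo, the display is the same in both arms, and the raters are blinded. An equal cue then largely cancels. This stands, and it limits the point to within-arm change plus a conditional risk to the contrast.

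The second reply is that the display is deliberate. Section 6.1.8 states its purpose, and a fixed reference against fading recall over 84 days is a reasonable aim. That also stands as a reason, but it does not make the baseline and follow-up conditions alike.

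A reader might infer four stronger things that the documents do not support:

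- **That the synopsis fixes the order of tasks.** At baseline it lists "pain, bruising and induration grading, FACE Q questionnaire, 2D Photography", and at Days 28 and 56 it lists photography first. These lists are not stated to be sequences. Table 4 and Appendix I list FACE-Q before photography, and the Day 84 synopsis entry is cut off in the text available.
- **That unmasked staff steer the answers.** Section 6.1.10 does not say who runs the display or whether it is discussed. Staff are unmasked at every visit with or without images, so this route is possible but not documented.
- **That FACE-Q is the only efficacy measure with a blinded rater.** Section 6.1.9 sends MRI images for central analysis and does not say whether that reader is masked.
- **That scores will be inflated by a known amount.** Direction, size and affected items are all assumed. Seeing an unchanged pair could lower a placebo subject's score.

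**Conclusion.** The point holds for the within-arm FACE-Q change. The follow-up and baseline scores are obtained under different conditions, and 10.5.1 and 10.5.5 report their difference by arm without a between-arm estimate.

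Its size cannot be fixed from the documents. Under the stated assumptions, an upward cue of 2 to 3 raw points from a raw sum of 20 adds 3 to 5 converted points to a change that would otherwise be 0.

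For the RZL-012 versus placebo contrast the documents show no bias. An equal cue leaves the difference at 0 when nothing has changed. With an assumed true gain of 10 raw points on active, an equal raw cue of 1 to 3 moves the difference only from 23 to between 24 and 28. A larger distortion needs a cue that differs by arm, for example because a side-by-side display magnifies a visible change.

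This concerns one descriptive secondary endpoint in a 28-subject study whose primary objective is safety. It is worth correcting because the correction changes little beyond the order of tasks within a visit.

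**What to change.** - **Section 6.1.10:** state that the FACE-Q is completed at every visit, baseline included, before any photograph is displayed and before the physician's assessment. Any comparison of images with the subject comes after the form is handed in.
- **Section 6.1.8:** remove the subject's satisfaction rating from the stated purpose of the images. Replace the reference to the screening visit, where no photograph is scheduled, so that it agrees with the baseline image used in 6.1.10 and 6.1.11.
- **Section 10.5.5:** state that the between-arm difference in FACE-Q change is the quantity interpreted, with the within-arm changes shown as supporting description.

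The questionnaire, photographs and visits stay the same. The real cost is that subjects lose the images as a reference when they answer, which gives up a stated function of the photographs. If the sponsor wants to keep a photographic reference, showing only the current image before the form at every visit, baseline included, would also match the conditions.
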